6.12. Safety Analyses

6.12.1. Treatment Compliance and Dose Intensity

The assigned dose of LY2157299 (or matched placebo) for every patient is 300 mg/day and the assigned dose for sorafenib is 800 mg/day for all patients in the combination arms. A prescribed dose is the dose the patient is prescribed to take in each cycle, including adjustments due to dose reductions or omissions within a cycle if prescribed by the investigator.

Treatment compliance is defined by the patient taking the study drug in mg as prescribed.

Dose intensity is expressed as a percentage of actual daily dose (mg) divided by assigned daily dose (mg) across all cycles, including the last cycle that may have been less than 28 days.

Treatment compliance and intensity information for LY2157299 (or placebo) will use collected pill counts of each tablet strength (150 mg and/or 80 mg if dose is reduced) at each cycle and the date of first dose and date of last dose in every cycle and study treatment discontinuation date. The pill counts will determine the extent of patient exposure to study drug. Similarly, treatment compliance and intensity information for sorafenib will use collected pill counts (tablet strength of 200 mg).

6.12.1.1. Planned dosing

Patients will be randomly assigned to one of the following arms shown in [Table JBAS.6.4](#).

Table JBAS.6.4. Treatment Regimens

				Number of Tablets Prescribed per Cycle^d
Daily Dose		Schedule	Time of Day	
Arm 1	150 mg BID LY	Daily 14 days on/14 days off	Morning and evening for 14 days ^{a,b} and then paused for 14 days	27 (Cycle 1) 28 (Cycle 2+)
Arm 2	150 mg BID LY ^c plus	Daily 14 days on/14 days off	Morning and evening for 14 days ^{a,b} with sorafenib and then paused for 14 days.	27 (Cycle 1) 28 (Cycle 2+)
	400 mg (2x200mg) BID sorafenib	Daily	Take in the morning and evening for 28 days	111 (Cycle 1) 112 (Cycle 2+)
Arm 3	LY-matched placebo plus	Daily 14 days on/14 days off	Morning and evening for 14 days ^{a,b} with sorafenib and then paused for 14 days.	27 (Cycle 1) 28 (Cycle 2+)
	400 mg (2x200mg) BID sorafenib	Daily	Take in the morning and evening for 28 days	111 (Cycle 1) 112 (Cycle 2+)

Abbreviations: BID = twice daily; LY = LY2157299; PK = pharmacokinetic.

Note: For patients who will have a Day 15 PK sample taken, the evening dose on Day 14 will be omitted to allow for a 24-hour time period between the Day 14 morning dose and the Day 15 PK sample.

^a In extenuating circumstances, the “on-study-drug” window for LY2157299 is allowable from Day 10 to Day 14.

^b Both study drugs should be taken on an empty stomach, at least 1 hour before a meal.

^c LY2157299 dose will be defined based on the results of the H9H-MC-JBAK study. Dose will either be 80 or 150 mg BID.

^d Assuming no prescribed omissions or adjustments.

LY2157299 300 mg/day will be administered orally 150 mg BID in 150-mg tablet form (300 mg total daily dose). A cycle (28 days) will be defined as an intermittent dosing regimen of 14 days of LY2157299 followed by 14 days without LY2157299 administration. All patients should not receive more than 14 consecutive days of LY2157299 dosing (28 tablets).

Sorafenib 800 mg/day will be administered orally 400 mg BID (2 tablets \times 200mg BID) for a 800 mg total daily dose. Sorafenib dosing will occur consistently throughout the 28-day cycle. All patients assigned to the combination arms should not receive more than 28 consecutive days of sorafenib dosing (112 tablets).

During Cycle 1 only, all patients should omit the Day 14 evening dose to ensure a 24-hour PK assessment. Visit/cycle start dates may vary \pm 3 days due to holidays, inclement weather, etc.

Planned dose adjustments and delays

If a toxicity related to LY2157299 is observed, the patient may be prescribed to omit one or more doses or have their dose reduced to 80 mg BID within the cycle. If this occurs, the patient may continue the next cycle on the full assigned dose (300 mg/day). However, if a patient experiences any of the events described in Section 9.4.1.1 of the Protocol, LY2157299 (or

placebo) will be omitted until the event resolves. If dosing is resumed, either in the same cycle or at the start of the next cycle, it will continue at a reduced dose of 80 mg BID (160-mg total daily dose). In case of a dose delay of LY2157299, patients can continue sorafenib treatment (at the investigator's discretion).

Clinically significant toxicities related to sorafenib described in Section 9.4.1.2 of the Protocol will result in dose delays or reductions. When dose reduction is necessary, sorafenib dosage may be reduced using the predefined dose levels:

- Dose level 1 (no reduction): 400 mg (2×200 mg) administered orally BID daily
- Dose level 2: 400 mg (2×200 mg) daily
- Dose level 3: 400 mg (2×200 mg) every other day
- If further dose reduction is required, the patient should be discontinued from sorafenib treatment.

At the discretion of the investigator, the sorafenib dose may be reescalated to the previous dose level 400 mg BID after the resolution of the AE.

In case of a dose omission/delay of sorafenib, patients can continue LY2157299 or placebo treatment up to total of 14 days (at the investigator's discretion). In case of discontinuation of sorafenib treatment, patients can still revive LY2157299 or placebo as per protocol (at the investigator's discretion).

At the discretion of the investigator, if a patient vomits within 30 minutes of taking a dose of LY2157299 or sorafenib, the dose should be repeated 1 time only that same day, if nausea/vomiting permits.

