**Table JBAS.9.2. Doses Adjustments for LY2157299**

Events Possibly Related to LY2157299	Adjustment
ANC <0.5 x 10  /L for longer than 7 days, or ANC <1.0 x 10  /L with a single temperature of >101°F/38.3°C or a sustained temperature of >100.4°F/38°C for >1 hour	LY2157299 will be omitted until the event resolves
Platelet count <25 x 10  /L	LY2157299 will be omitted until the event resolves
CTCAE Grade 3 or 4 nonhematologic toxicity	LY2157299 will be omitted until the event resolves

Abbreviations: ANC = absolute neutrophil count; CTCAE = Common Terminology Criteria for Adverse Events.

- Nonhematologic toxicity must resolve to CTCAE Grade 0, 1, or baseline level before resuming treatment (with the exception of alopecia, fatigue, skin rash, nausea, vomiting, constipation, or diarrhea that can be controlled with treatment).
- Hematologic toxicity must resolve to a level that, in the opinion of the investigator, is reasonable to allow for continuation of treatment.

If dosing is delayed for >2 weeks for treatment-related AEs, the patient should be withdrawn from the study treatment. Patients who do recover within the 2-week time frame may have the dosage reduced to 160 mg/day (or 80 mg/day if selected dose for the combination is 160 mg/day).

In case of a dose delay of LY2157299, patients can continue sorafenib treatment (at investigator discretion).

No patient will have his/her LY2157299 dose reduced more than once. Reescalation to the previous LY2157299 dose is acceptable in the absence of continuing or cardiac toxicities. If subsequent LY2157299 dose reduction is required after reescalation, the patient must be maintained at the reduced dose level for all remaining cycles.

If moderate or severe heart valve toxicities are observed, the patient must immediately be discontinued from the treatment (for definitions see [Attachment 14](#), including references on the echocardiographic assessment based on the Guidelines of the American and European Societies of Cardiac Echocardiography). Exceptions to this rule must be approved by the ERBs and Lilly.

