6.12.9. Protocol Violations

Significant protocol violations that potentially compromise the data integrity and patients' safety are listed by treatment group for all randomized patients.

Appendix 1 lists the categories of significant protocol violations, the detailed description of each violation within the category, and the method to identify each violation. Further details of study monitoring are in the Study Specific Monitoring Requirements (SSMR) document.

All data collected on the CRF will be checked programmatically for violations. Actual details specifying the programming methods will be given in the ADaM and table, figure, listing (TFL) specifications. Protocol violations that are documented in the monitoring database will be exported to an Excel file for import by statistics. Patients with significant violations may be excluded from the per-protocol population.

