LY 2157299 dose reductions not occurring as specified	Identified both by CRA during monitoring and programmatically. dose reduction did not occur after qualifying AE >1 dose reduction (without reescalation) during the course of the study or, if reescalated, >1 dose reduction after reescalation during the course

	of the study >1 reescalation occurs during the course of the study Patient not withdrawn from LY2157299 if dosing is delayed for >2 weeks for treatment-related AEs
Lack of subject compliance with treatment	Identified both by CRA during monitoring and programmatically. List any subjects with compliance per cycle that is <80% or >120%.
Prohibited concomitant therapy	Identified both by CRA during monitoring and programmatically by verifying no prohibited medications are in CRF data. other anti-cancer therapy (chemotherapy, target therapy, radiotherapy, except palliative radiation to non-target lesions); immunotherapy; hormonal cancer therapy; experimental/investigational medication; Rapamycin analogues; Increased immunosuppressive therapy (patients on maintenance immunosuppressive therapy after liver transplant are eligible); At the discretion of the investigator, hormone-refractory prostate cancer patients who are stable on GnRH agonist therapy and breast cancer patients who are stable on antiestrogen therapy (for example, and aromatase inhibitor) may have that treatment continued while they are enrolled in this study.
Failure to perform PK collections	Identified both by CRA during monitoring and programmatically. Note: only collections “not done” are considered significant protocol violations.
Failure to perform safety assessments	Failure to perform safety procedures or missing safety measurements per requirements in Study Schedule (Attachment 1 in Protocol). Hematology/chemistry; CT and MRI ECG ECHO and Doppler Identified both by CRA during monitoring and programmatically. Note: only collections “not done” are considered significant protocol violations.
Failure to perform efficacy assessments	Failure to perform efficacy procedures or missing efficacy measurements. Radiological Tumor Assessments per RECIST and mRECIST. Palpable/visible (as applicable). Identified both by CRA during monitoring and programmatically. Note: only collections “not done” are considered significant protocol violations.
Violation of discontinuation criteria	

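### The SAP treats LY2157299 dose reduction on resumption as mandatory where the protocol leaves it optional, so a patient managed as the protocol allows can be listed as a significant violator

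*SAP*

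**What the plan says.** Protocol section 9.4.1.1 covers events considered possibly related to LY2157299: prolonged severe or febrile neutropenia, a very low platelet count, and Grade 3 or 4 non-hematologic toxicity. Table JBAS.9.2 gives the same single adjustment for each: "LY2157299 will be omitted until the event resolves". The text under the table withdraws a patient from treatment when a delay for treatment-related events exceeds two weeks. For the others it says: "Patients who do recover within the 2-week time frame may have the dosage reduced to 160 mg/day", with a lower figure had 160 mg/day been chosen for the combination.

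SAP section 6.12.1.1 first deals with LY2157299 toxicity in general. Doses may be omitted or lowered within a cycle, and the full assigned dose may follow in the next. It then turns to a separate case: "if a patient experiences any of the events described in Section 9.4.1.1 of the Protocol". Here the drug or placebo is omitted until resolution, and then: "If dosing is resumed, either in the same cycle or at the start of the next cycle, it will continue at a reduced dose", given as 80 mg BID.

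SAP Appendix 1, Table 1, describes the significant protocol violations. Its row on LY2157299 reductions includes the criterion "dose reduction did not occur after qualifying AE", to be found both by the site monitor and by program. SAP section 6.12.9 has significant violations listed by treatment group for all randomized patients, and adds: "Patients with significant violations may be excluded from the per-protocol population". SAP Table JBAS.6.2 defines the per-protocol population by the absence of major deviations. It makes efficacy analyses on that population a possibility only, and assigns efficacy analyses other than tumor response to the randomized population.

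**The concern.** A violation check should measure conduct against what the protocol requires. Here the SAP appears to measure it against a stricter rule of its own. An investigator who follows protocol 9.4.1.1 and resumes LY2157299 without a reduction has departed from nothing in the protocol, yet seems to meet a criterion for a significant violation.

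Two outputs are at stake. The violation listing would count permitted management as misconduct, whether or not any per-protocol analysis is run. And if a per-protocol analysis is run, its membership would depend partly on a drafting mismatch, applied to patients selected by an adverse event after randomization.

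**Working it through.** There is no stated figure to reproduce. The check sets the passages side by side.

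1. **Same events?** Yes. SAP 6.12.1.1 defines its case by pointing to protocol section 9.4.1.1.
2. **Same reduced level?** Yes. SAP 6.12.1 gives the assigned LY2157299 dose as 300 mg/day. The SAP's reduced dose is 2 × 80 mg = 160 mg/day, the protocol's figure for that assigned dose. The conflict is only whether the reduction is optional (*may*) or fixed (*will*).
3. **Loose drafting in the SAP?** Unlikely. The same paragraph allows a return to the full dose after other LY2157299 toxicities, then changes to an unconditional statement for the 9.4.1.1 events.
4. **A version difference?** No. SAP 6.1 refers to protocol version 1.0, and the summary of amendment (a) lists no change to 9.4.1.1. SAP Version 2 did edit Appendix 1, adding the criterion on withdrawal after a delay of more than two weeks. That criterion now sits in the same row as the reduction check, but the mismatch stayed.
5. **What is a qualifying AE?** The SAP does not say. The Appendix 1 row on failure to omit study drug lists the 9.4.1.1 events. Because failure to omit has that row to itself, the reduction row concerns what happens on resumption. The natural reading is that the 9.4.1.1 events qualify.
6. **A test case.** A patient assigned 300 mg/day has a Grade 3 non-hematologic toxicity possibly related to LY2157299, omits the drug, recovers within two weeks and resumes at 300 mg/day.

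| Text | Status of this patient |
|---|---|
| Protocol 9.4.1.1 | No departure: reduction was optional |
| SAP 6.12.1.1 | Departure: reduction stated as certain |
| SAP Appendix 1 | Significant violation, on the reading in step 5 |
| SAP 6.12.9 | Listed by treatment group; exclusion from per-protocol possible |
| SAP Table JBAS.6.2 | Unclear: turns on *major*, which the SAP does not tie to *significant* |

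7. **Size.** Planned arms are 30, 60 and 30. One exclusion removes 1/60 = 1.7% of the combination arm, or 1/30 = 3.3% of the monotherapy or control arm. The number of exclusions would be the number of patients with a qualifying event who resume unreduced and are then judged excludable. None of these counts is in the documents. The earlier HCC study (protocol 5.1.5.1) reports only its most common related Grade 3/4 events, for example 2 of 106 patients each for GI bleeding and fatigue. It studied monotherapy in mostly pretreated patients and does not show who resumed at which dose, so it cannot supply the number.
8. **What does not move.** The compliance percentage is unaffected, because SAP Table JBAS.6.5 takes the prescribed dose from the case report forms.

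**The case against.** The strongest reply is that no decision depends on this. The primary conclusion is a posterior probability above 0.84 under the strong prior (SAP 6.9.1), analyzed on the randomized population. A per-protocol effect needs a judgement that the deviation is major, a choice to exclude, and a choice to run the analysis. This stands, and it limits the point to secondary output. It does not reach the violation listing, which is produced for all randomized patients.

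A second reply is that the Appendix 1 row concerns reductions not made as specified. If that means as the protocol requires, an optional reduction cannot be violated, and the monitor's review would catch a false flag. This stands in part: the flag is likely, not certain. But SAP 6.12.1.1 is itself a specification, and it says the reduction happens. A programmer working from the SAP would have no reason to exempt these patients.

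Two stronger readings are tempting, and the documents support neither:

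- A reader might infer that exclusions would fall mainly on the arms receiving active LY2157299 and so bias the comparison in a known direction. But the SAP's omission rule covers placebo as well, investigators are blinded between Arms 2 and 3 (protocol 9.5), and an event whose cause the investigator cannot determine is classed as related (protocol 10.3.1). Sorafenib toxicity in the control arm could therefore trigger the same rule. No rates by arm are given.
- A reader might infer that the protocol also contradicts itself, because it says "No patient will have his/her LY2157299 dose reduced more than once" and then provides for a reduction after re-escalation. But it also says "Reescalation to the previous LY2157299 dose is acceptable in the absence of continuing or cardiac toxicities", and the sentences can be read together as one reduced level to which a patient may return. Appendix 1 counts reductions consistently with that reading.

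**Conclusion.** The inconsistency is real. For the same events and the same reduced dose level, the protocol permits a reduction and the SAP states it as certain. The violation check appears to follow the SAP, so a patient treated within the protocol could be reported as a significant violator and, at discretion, lose per-protocol status.

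The conclusion rests on one assumption: that the undefined qualifying AE means the events of protocol 9.4.1.1. The consequence is confined to the violation listing and an optional supplementary analysis. The number of patients affected, their distribution across arms and any effect on a per-protocol hazard ratio cannot be determined from the documents. The correction is worth making before lock because the rule as written can mislabel patients and costs little to align. Which dosing rule is right is for the sponsor to settle.

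**What to change.** Before database lock, and before per-protocol membership is fixed:

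- Reconcile protocol 9.4.1.1, SAP 6.12.1.1 and the reduction row of SAP Appendix 1 so that all three state the same rule.
- Define the qualifying AE in Appendix 1, by reference to protocol 9.4.1.1 if that is what is meant.
- Program the check to flag only departures from what the reconciled protocol text requires.
- State in SAP 6.12.9 or Table JBAS.6.2 how significant violations map to the major deviations that define the per-protocol population.

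If the reconciliation is made on the SAP side, the cost is a few sentences and one programming rule, with no new data. If the protocol text is what changes, a protocol clarification or amendment is needed as well.

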6.12.1.2. Data Collection Process

Exposure days and prescribed dose

The first dose of Cycle 1 is recorded on the Study Treatment PK - Cycle 1 Day 1 Dose 1 CRFs (EX1001_F1 and EX1001_F16 for LY2157299/Placebo and sorafenib, respectively). The first dose for Cycles 2+ is recorded on the Study Treatment PK - Day 1 CRFs (EX1001_F6 and EX1001_F15 for LY2157299/Placebo and sorafenib, respectively). These forms contain the start date and time, whether the start of the cycle was delayed (Cycles 2+), dose per administration, and dose frequency for each cycle. If there is a dose reduction, the end date and time on the Study Treatment Changes CRFs (EX1001_F7 and EX1001_F13) will reflect the last dosing date/time at the original prescribed dose (for example, the last day the patient took 300 mg/day of LY2157299). The site then enters the new start date and time which will be the day the patient started at the reduced dose (for example, 160 mg/day of LY2157299). If there is a dose omission (whether prescribed or due to patient non-compliance), the start and end dates and times of the missed doses will be recorded on the Exposure Dose Omission CRFs (EX1001_F25 and EX1001_F24). Finally, the Study Treatment Last Dose CRFs (EX1001_F2 and EX1001_F34) will contain the date/time, dose and frequency of the last day in the cycle that the subject took their prescribed dose (for example, if LY2157299 was reduced, 160 mg/day).

Pill counts

At the end of each cycle and the beginning of the next cycle, the number of tablets dispensed and returned of each tablet strength (150mg and/or 80mg tablets for LY2157299 or 200mg tablets for sorafenib) will be recorded on the Study Treatment Compliance CRFs (DA1001_F1 and DA1001_F2).

6.12.1.3. Derivations

Subject compliance with study medication will be assessed by reconciling the number of tablets of each tablet strength dispensed at each cycle with the number of tablets of each strength returned at each subsequent cycle through the end of the study treatment. The number of tablets of each strength will be multiplied by the tablet strength to give the **actual total drug taken** in mg. (Note: This amount could alternatively be derived by taking the sum of the actual days dosing occurred (subtracting omitted days from the dosing interval) multiplied by the actual dose per administration and frequency in each dosing interval). This will be compared with the **prescribed total drug taken** by calculating the number of tablets of each strength expected to be taken (prescribed tablets) multiplied by their tablet strength. The prescribed total dose is based on the days for each prescribed daily dose in the dosing interval (exposure days), accounting for any prescribed dose adjustments (delays, omissions, or reductions). The total drug taken relative to the total prescribed will be summarised for each cycle and overall for each patient. A patient will be considered compliant with the study therapy protocol if the total drug taken indicates the patient took between 80% and 120% of the planned LY2157299 dose in mg during the cycle of study therapy.

Dose intensity takes the total drug taken (mg) (from above) in the study divided by the number of days on study treatment (that is, **average actual daily total** in mg) compared to the **assigned total drug** (mg) divided by the **expected number of days on study**, and expressed as a percentage. The assigned total drug is calculated from the sum of the number of cycles completed times the expected number of days of dosing in each cycle (for example, for LY2157299, 13.5 for cycle 1, 14 for every other completed cycle and the number of exposure days of the last cycle on treatment) multiplied by the assigned daily dose at Cycle 1 (for example, for LY2157299, 300 mg). The expected number of days from first dose to study treatment discontinuation is the number of cycles completed times 28 (the expected cycle length) plus the number of days prior to study treatment discontinuation in the last cycle. Dividing assigned total dose by the expected number of days prior to study treatment discontinuation gives the expected daily dose in mg. This calculation allows for dose delays.

The dose intensity per patient will be summarised using descriptive statistics.

The following compliance and dose intensity definitions ([Table JBAS.6.5](#)) will be used to calculate compliance and intensity for each cycle and overall for each patient:

Table JBAS.6.5. Compliance and Dose Intensity Definitions

Term	Definitions or Rule
Compliance rate (%)	100 x actual drug taken (mg) / total drug (mg) prescribed Calculated for each cycle and overall for each patient
Dose Intensity (%)	100 x actual daily dose (mg) / assigned daily dose (mg) Calculated for each cycle and overall for each patient Note: Daily dose here is determined by assigned or actual cycle length, not just the daily dose given in the dosing period
Components required for calculations above	Definitions or Rule
Total actual drug taken (mg)	Per patient, per cycle, equal to ((the number of tablets dispensed – number of tablets returned)*tablet strength) summed across tablet strength Per patient, the total drug taken per cycle summed over all cycles.
Prescribed exposure days	Days in the dosing interval – days omitted due to non-compliance Note: reasons due to non-compliance are any reasons for an omitted dose that are not due to adverse event (AE) (for example, patient decision or scheduling conflict)
Total expected (prescribed) drug (mg)	Per patient, per cycle: sum of (prescribed exposure days x daily prescribed dose) across different prescribed daily doses Daily prescribed dose is taken from 'Cycle 1 Day 1 Dose 1' and 'Study Treatment Changes' clinical (case) report forms (CRFs) Per patient, the total prescribed drug per cycle summed over all cycles
Total Assigned Drug (mg)	Per patient, per cycle: LY2157299: Sum of (expected days exposure in cycle*300) where expected days exposure in Cycle 1=13.5, expected days exposure in Cycle 2+ = 14 and expected days exposure in the last incomplete cycle = date of last dose in cycle – date of first dose of cycle +1 Per patient, the total assigned drug per cycle summed over all cycles Sorafenib: Sum of (expected days exposure in cycle*800) where expected days exposure in Cycle 1 is 27.5, expected days exposure in Cycle 2+ = 28 and expected days exposure in the last incomplete cycle = date of last dose in cycle – date of first dose of Cycle +1 Per patient, the total assigned drug per cycle summed over all cycles
Total days of actual exposure at each prescribed dose	Per patient, per cycle, per dose: Days of exposure = sum (date of last dose – date of first dose +1) taken from the chronology of dates from 'Cycle 1 Day 1 Dose 1', 'Study Treatment Changes' and 'Study Treatment Last Dose' CRFs The total days of actual exposure over all doses prescribed during a cycle should be: LY2157299: 13.5 for Cycle 1 and 14 for Cycle 2+ (unless planned omission or incomplete last cycle). Sorafenib: 27.5 for Cycle 1 and 28 for Cycle 2+ (unless planned omission or incomplete last cycle). Total days of actual exposure for a patient in the study is the sum of exposure days across all cycles

Compliance and Dose Intensity Definitions

Term	Definitions or Rule
Total days expected to be on study given number of cycles completed and length of last cycle on study treatment (excludes any dose delays)	
Per patient, per cycle: 28 for all completed cycles and (date of study treatment discontinuation- date of first dose in last cycle+1) for the last cycle on study treatment
 
Per patient:
 
Days expected to be on study=(number of started cycles-1)*28 + (date of study treatment discontinuation- date of first dose in last cycle+1)

Total actual days on study (includes dose delays)	
Per Patient, per cycle: Date of first dose in cycle (x+1) – date of first dose in cycle (x) for all cycles except the cycle started.
 
Number of days on last cycle started = date of study treatment discontinuation – date of first dose in last cycle
 
Per patient: Date of study treatment discontinuation – date of first dose +1 (should be equivalent to the sum of days on study across cycles)

Assigned daily dose	
Per patient, per cycle: Total assigned drug/total expected days for each cycle
 
Per patient: Total assigned drug across cycles/total days expected to be on study across cycles

Actual daily dose	
Per patient, per cycle: Total actual drug taken/total actual days for each cycle
 
Per patient: Total actual drug across cycles/total actual days on study across cycles
 
Note: This is NOT the same as the sum of the assigned daily dose per patient per cycle/number of cycles.

Using the compliance and dose intensity derived for each patient as above, compliance and dose intensity will be summarised for LY2157299 and sorafenib by the following listing and table:

- Listing of oral dosing information including tablets distributed, returned, taken and prescribed at each cycle, dose adjustments, omissions and cycle delays, percent compliance per cycle and overall per patient.
- Summary of dose intensity per patient.

Further exposure summaries of LY2157299 and sorafenib include a summary of the number of patients completing each cycle and a summary of study drug administration including the number of patients with doses given as planned, with doses that were reduced, and with cycle delays.

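### SAP Table JBAS.6.5 takes patient-skipped days out of the compliance denominator, so a recorded mid-course skip scores 100%, contrary to SAP 6.12.1 and 6.12.1.3

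*SAP*

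**What the plan says.** SAP 6.12.1 defines the prescribed dose as what the patient is told to take in each cycle, "including adjustments due to dose reductions or omissions within a cycle if prescribed by the investigator". It then says: "Treatment compliance is defined by the patient taking the study drug in mg as prescribed". SAP 6.12.1.3 repeats the principle, basing the prescribed total on exposure days "accounting for any prescribed dose adjustments (delays, omissions, or reductions".

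Table JBAS.6.5 in the same section gives the definitions to be used in the calculation. The compliance rate is 100 x actual mg / prescribed mg. Actual mg is a pill count (tablets dispensed minus returned, times strength). Prescribed mg is prescribed exposure days times the daily prescribed dose. Prescribed exposure days are "Days in the dosing interval – days omitted due to non-compliance". The note to that row reads "reasons due to non-compliance are any reasons for an omitted dose that are not due to adverse event (AE", with the patient's own choice and scheduling clashes as its examples.

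SAP 6.12.1.3 sets the acceptable range: a patient is compliant if "the patient took between 80% and 120% of the planned LY2157299 dose in mg during the cycle of study therapy". SAP Appendix 1 lists anyone outside 80% to 120% in a cycle under significant protocol violations. SAP 6.12.9 allows such patients to be left out of the per-protocol population.

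**The concern.** The text and the table handle the two kinds of omission in opposite ways. Under the text, a hold ordered by the investigator lowers the target, while a dose the patient chooses to miss does not. Under the table, the missed dose lowers the target and the AE hold does not.

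The numerator is a pill count, so skipped days are already absent from it. Taking the same days out of the denominator cancels them, and non-compliance that the site records cannot lower the compliance rate. A programmer following the table would produce a check that misses the patients it is meant to find. It might also flag some who followed instructions.

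**Working it through.** **Inputs.** LY2157299 at 300 mg/day in 150 mg tablets (SAP 6.12.1); 14 dosing days in Cycle 2 onward and 13.5 in Cycle 1 (Table JBAS.6.5); the compliance formula above.

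**The plan's own figure first.** Table JBAS.6.4 gives 28 LY2157299 tablets per cycle from Cycle 2 and 27 in Cycle 1. Check: 14 x 300 / 150 = 28 and 13.5 x 300 / 150 = 27. Both agree. The SAP gives no worked compliance percentage to reproduce.

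**Two denominators.**
- Table: (interval days - non-AE omitted days) x 300.
- Text: (interval days - prescribed omitted days) x 300.

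**Patient skips mid-course, Cycle 2 onward** (full course 14 x 300 = 4200 mg):

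| Skip | Actual mg | By Table JBAS.6.5 | By the text |
|---|---|---|---|
| 3 days, recorded | 11 x 300 = 3300 | 3300/3300 = 100% | 3300/4200 = 78.6% |
| 4 days, recorded | 10 x 300 = 3000 | 3000/3000 = 100% | 3000/4200 = 71.4% |
| 7 days, recorded | 7 x 300 = 2100 | 2100/2100 = 100% | 2100/4200 = 50.0% |
| 7 days, not recorded | 2100 | 2100/4200 = 50.0% | 2100/4200 = 50.0% |

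Under the table, the same 7-day skip scores 100% or 50.0% depending only on whether the site completes the omission form.

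**AE hold mid-course, same-dose restart.** This step assumes that the dosing interval runs from first to last dose at a given prescribed dose and so spans the hold. The hold then stays in the table's denominator: 2 days 3600/4200 = 85.7%, 3 days 3300/4200 = 78.6%, 4 days 3000/4200 = 71.4%. The text gives 100% each time. Three days is the shortest whole-day hold that falls below 80%. In Cycle 1 a 3-day hold gives 21/27 tablets = 77.8%.

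**Where the AE effect disappears.**
- Hold on Days 6 to 8, then 80 mg BID on Days 9 to 14. The date chronology most naturally gives two intervals with the gap in neither. Actual and prescribed are both 5 x 300 + 6 x 160 = 2460 mg, so 100%.
- Hold on Days 12 to 14, to the end of the course. The interval ends at the last dose on Day 11, so 3300/3300 = 100%.

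**Early self-stopping.** On the same first-to-last-dose reading, a patient who stops by choice after Day 7 has a 7-day interval and scores 2100/2100 = 100%. Reversing the subtraction would not correct this. The interval itself has to be defined.

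**The case against.** The strongest reply concerns the AE hold. The SAP does not define the dosing interval. The 6.12.1.3 text asks for prescribed omissions to be allowed for, and the actual-exposure row of Table JBAS.6.5 makes an exception for a planned omission. If the interval is already net of prescribed holds, the held patient scores 100%. The spanning reading has support, because 6.12.1.3 describes an alternative numerator that subtracts omitted days from the interval, but it remains an assumption. The case is also narrow. A same-dose restart is open because "the patient may be prescribed to omit one or more doses or have their dose reduced to 80 mg BID within the cycle", and Protocol 9.4.1.1 makes reduction after recovery optional. For the events named in Protocol 9.4.1.1, however, SAP 6.12.1.1 says of resumed dosing that "it will continue at a reduced dose of 80 mg BID". This objection stands, so the AE result is secondary and conditional.

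A second reply is that the range sentence in 6.12.1.3 speaks of the planned dose, and SAP 6.7 compares tablets taken with the number expected or planned. Against a full planned course, a 3-day skip and a 3-day hold both score 78.6%. That still does not give the skip 100%, so it does not rescue the table. It shows that the SAP also uses *planned* where it needs *prescribed*.

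A reader might go on to infer that sorafenib holds would breach the 80% limit. The documents do not settle that. The range sentence in 6.12.1.3 names only LY2157299, and Appendix 1 names no drug. The SAP's sorafenib target for Cycle 1 is also inconsistent: Table JBAS.6.4 says 111 tablets, but 27.5 days x 800 / 200 = 110.

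A reader might also infer that the efficacy results are distorted. Primary OS uses all randomized patients. Dose intensity is built from assigned drug and does not use this row. The safety population depends only on receiving a dose. The patient listing shows omissions beside the percentage, and site monitors check compliance as well. Exclusion from the per-protocol set is discretionary, and analyses on that set are optional.

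**Conclusion.** The contradiction is real and the skip result is firm. For LY2157299 in Cycle 2 onward, recorded mid-course skips of 3, 4 or 7 days score 100% where the SAP's text gives 78.6%, 71.4% and 50.0%. This requires only that the skip falls within the course and is entered on the omission form.

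The AE-hold result (78.6% instead of 100% for 3 days) holds only if the interval spans the hold and dosing restarts mid-course at the same dose. Holds resumed at 80 mg BID are not affected.

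The consequences are confined to the compliance percentages in the patient listing, the Appendix 1 compliance item and possible exclusion from the per-protocol set. The documents give no frequency of skips or holds, so neither the number of patients affected nor any difference between arms can be estimated. The correction is worth making because the rule as written defeats its own check and is cheap to repair.

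**What to change.** In Table JBAS.6.5, define prescribed exposure days as the scheduled dosing days in the cycle minus days omitted on prescription. Scheduled days are 13.5 in Cycle 1 and 14 from Cycle 2 for LY2157299, and 27.5 and 28 for sorafenib. Shorten them only for a prescribed stop or an incomplete last cycle. Keep omissions by patient decision or for scheduling reasons, including early self-stopping, in the denominator. In the range sentence of 6.12.1.3, change *planned* to *prescribed*, and use this rate for the Appendix 1 compliance item.

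Results for LY2157299 in Cycle 2 onward after the change: 3-day patient skip 3300/4200 = 78.6%; 3-day AE hold 3300/3300 = 100%; self-stop after Day 7 2100/4200 = 50.0%.

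SAP 6.12.1.2 puts prescribed and patient omissions on the same form and does not say whether the form shows who initiated them. If it does not, use the AE versus non-AE reason, which the table already relies on, as the working definition of a prescribed omission. The cost is one redefined table row and one word, with no new data under that working definition. The small downside is that a patient who stops without instruction because of an AE would be treated as having followed a prescribed hold.
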